#### **1.0 Introduction**

Incidence and mortality rates in liver cancer are on the rise in the U.S[1]. By 2030, liver cancer is expected to exceed breast cancer as the second leading cause of cancer death in the U.S[2]. Up to 30% of liver cancer cases are attributed to Hepatitis B (HBV) and/or Hepatitis C (HCV) viral infection, though the fraction of liver cancer cases in African American and Asian patients attributed to chronic HBV or HCV is much higher, closer to 40%-50%[3]. In Caucasians and Hispanics, HCV infection is considered a second leading cause of liver cancer, behind only diabetes and obesity[4]. In the State of Pennsylvania, racial trends in liver cancer, HBV, and HCV are similar to those in the U.S[5]. In the Temple University Health System, which serves primarily African American and other minority groups, incidence rates of liver cancer are the highest of any cancer site.

Liver cancer incidence rates could be significantly lowered by reducing rates of HCV and HBV infections[6]. Treatments with high cure rates exist for HCV, and HBV can be prevented through vaccination[7]. Further, HCV and HBV infection are often contracted through risk behaviors (i.e., sexual activity, drug use, unsanitary tattoo/nail salon practices) that could be modified through educational interventions and policies. However, rates of both liver cancer and HCV continue to rapidly increase, suggesting that available, evidence-based interventions are not reaching the most vulnerable, high risk populations. There is a disconnect between translation of findings from discovery into population impact, and the disproportionate rates of HBV, HCV, and liver cancer across racial groups suggest health inequities contribute to the growing burden of liver disease in this country.

In this study, we propose to bridge the gap between evidence and action and combat rising liver cancer rates attributed to Hepatitis B and C infection in Philadelphia by identifying neighborhoods with higher than expected rates of liver cancer and related risk factors and administering an educational intervention in those communities, working with existing community partners at Fox Chase Cancer Center. In this proposal, we will generate new methods for identifying smaller communities or geographic areas (at the census tract level) in need of liver-cancer related interventions. This is an improvement over existing studies that focus mostly on single risk factors for disease and targeting counties, which are often too large to implement public health programs[8]. By dually considering area-level measures of disparity (i.e. race/ethnicity, immigration, poverty, etc. from the U.S. Census) WITH the distribution/cooccurrence of liver cancer, HBV, and HCV, we hope to also shed light on disparities in liver cancer. We hypothesize that communities carrying the greatest burden of liver disease (liver cancer/HCV/HBV) AND health disparities, if targeted, could lead to the greatest declines in liver cancer over time. Further, community partners that work with the Fox Chase Office of Community Outreach requesting cancer education sessions via our Community Speaker's Bureau for their community programs will be approached with this new liver cancer initiative. We will begin with partner sites identified via geocoding as well as regions where we need to establish new partnerships. Partners will be informed of the project, its objectives and if interested, we will deliver the educational session about person-level liver cancer risk factors and how to reduce liver cancer risk, as well as some background on liver cancer rates and neighborhood research. We will then administer pre-post tests to participants to test knowledge, attitudes, and intentions, and will disseminate liver cancer brochures from the American Liver Cancer Foundation to relevant community groups. The use of surveillance data and the application of geospatial analytics to guide interventions that benefit populations more efficiently is a strategy that defines precision public health[9].

## 2.0 Objectives/Aims

Aim 1 (Similar to currently approved IRB #17-9031): Conduct a geographic scan of liver cancer and related risk factors (age, race/ethnicity) for the entire State of PA by census tract in order to dually *identify* neighborhoods in Philadelphia with greater disease/disparity burdens than expected compared to the State and to *inform* where liver cancer-related educational interventions may be most needed. *Hypothesis:* Enhanced spatial tools/metrics (that couple disease rates & area-level measures of disparity) will inform resource allocation through more precise identification/targeting of communities in need.

[figure not shown]
**Aim 2**: To identify and/or establish community partnerships in "high-risk" areas to collaborate with, delivering and evaluating educational sessions.

**Impact:** Our focus on geospatial, area level risk factors will provide novel insights into liver cancer disparities. We take an innovative precision public health approach where the successful primary and secondary prevention of liver cancer could be monitored in areas selected for intervention in future studies.

#### 3.0 Background/Rationale

**A. Precision Public Health Approach in Liver Cancer**. As outlined in currently approved IRB 17-9031, the use of data to guide interventions that benefit populations more efficiently is a strategy referred to as precision public health. Precision public health requires primary

surveillance data, rapid application of sophisticated analytics to track the geospatial distribution of disease, and the capacity to act on this information in the form of interventions. In this proposal, we plan to use surveillance data from the Pennsylvania (PA) Cancer registry, the PA and Philadelphia Infectious Disease HBV/HCV registries and the U.S. Census in order to identify fewer and smaller geographic areas that are carrying the greatest disease burden of liver cancer, as well as a high burden of determinants of health disparities. We will create new combinations of disease metrics and summary scores for determinants of disparity in order to estimate the disease/disparity burden in each census

tract in Pennsylvania. In an attempt to maximize limited resources, our goal is to select the fewest number of "in need" areas, where existing educational and screening interventions are likely to have the greatest impact on decreasing liver cancer rates.

**B. Liver Cancer Statistics.** The incidence rates of liver cancer have tripled over the past three decades. Due to a very poor prognosis, liver cancer is the fifth most common cause of cancer death in the United States. Hepatocellular carcinoma (HCC) is the major histological subtype, accounting for up to 80% of all cases[10]. In Pennsylvania, the incidence and mortality rates of liver cancer have been climbing each year since 2003. In our catchment area, incidence rates of liver cancer are the highest of any cancer site in the Philadelphia area. Thus, the burden of liver cancer needs to be addressed.

C. Liver Cancer and Hepatitis. Risk factors for liver cancer are largely understood, with up to 70% of liver cancer cases being attributed to modifiable factors, including drug/alcohol use, obesity, diabetes, and viral infection with Hepatitis B/C[4]. Despite these risk factors being largely addressable through early detection, vaccination, treatment, and lifestyle interventions. liver cancer continues to rise in the U.S., particularly in minority populations) [4]. Hepatitis B and C account for 32% of liver cancer cases in the U.S. In African American and Asian populations, HBV and HCV account for 40-50% of liver cancer cases, whereas in Hispanics and Caucasians, HBV and HCV account for closer to 20% of cases. In a study of Philadelphia residents between 2003-2012, individuals with HCV and HBV accounted for close to 40% of all liver cancer diagnoses. Further, HCV-infected patients were also 2.8 times more likely to have liver cancer detected before age 65 and to have an earlier age of death than individuals without HCV. For Philadelphia males and non-Hispanic blacks, HCV was more common and more often associated with liver cancer diagnosis and death at a younger age. For Asians in Philadelphia, HBV was more common and more often associated with liver cancer diagnosis and death. Given the contribution of HCV and HBV to liver cancer in our area, widespread public health actions to prevent HCV and HBV infection could have a substantial effect on the burden of liver cancer in Philadelphia. Thus, in this proposal, we focus on identifying geographic areas (census tracts) that carry the greatest burden of liver cancer, and will be creating an educational session to review risk factors for liver cancer and how to decrease risk.

D. Disparities in Liver Cancer. Beyond race/ethnicity, individual-level socioeconomic status (SES) (e.g., education, income, employment), as well as area-level SES conditions (i.e., neighborhood socioeconomic deprivation), are also believed to contribute to liver cancer[11]. Liver cancer patients are more likely to live in deprived-socioeconomic conditions, and studies show that these area-level socioeconomic associations may result from the geographic distribution of individual risk factors associated with liver cancer, such as low educational attainment. This is important because studies have shown differences in area-level determinants of disparity by race, i.e. African Americans living in neighborhoods with high poverty (but not areas with high unemployment) and Hispanics living in areas of low educational attainment have higher rates of liver disease. Further, additional determinants of disparity (beyond race/ethnicity, education, income, employment) that are dually related to health outcomes and can provide useful information for intervention development, also warrant further study. These determinants include immigration status, literacy, transportation, and housing (Table 1). In this study, we more comprehensively evaluate determinants of disparity in liver cancer. We do not plan to investigate associations between determinants of disparity and liver cancer, but will quantify the prevalence of determinants of disparity in small geographic areas (i.e. census tracts) and use that information to create an overall disparity metric or score. This new disparity metric can be referenced and used to determine 1) which areas with high rates of liver disease (liver cancer, HCV, and/or HBV) also have a high disparity score (with the hypothesis that targeting fewer areas with higher disease and disparity scores will result in maximizing limited resources): 2) what determinants (i.e. education, employment, literacy, etc) are driving the low disparity score in each area, which can inform the type of intervention/intervention materials needed for designated high risk areas(i.e. where should Spanish educational interventions be offered, etc).

**E. Recommendations for the Primary and Secondary Prevention of Liver Cancer**. While recommendations for liver cancer do vary, the National Comprehensive Cancer Network panel recommends screening with ultrasound and alpha fetoprotein (AFP; a liver cancer blood biomarker) testing every 6 to 12 months for patients at risk for liver cancer. At risk populations are defined as those with liver cirrhosis and hepatitis B. Liver cirrhosis can be caused by HBV

and HCV infections. Screening tests for HCV and HBV involve blood test screening for HCV and HBV antibodies. For those diagnosed with HCV, curative treatment is recommended. One problem is the majority of HBV/HCV carriers do not know they are infected. Thus, they can unknowingly spread the virus (through risk behaviors such as unsanitary needle use). Further, those with chronic HCV and/or HBV infection are often diagnosed with advanced liver disease (cirrhosis) and/or advanced liver cancer. Patients diagnosed with early stage liver cancer survive more than 5 years. However, the majority of liver cancer cases are diagnosed with advanced stage liver cancer where the average survival is less than one year. Given the contribution of HBV and HCV to liver cancer incidence, interventions that provide education about hepatitis, who is at risk, and how it is contracted, will likely have an impact on liver cancer incidence and mortality rates. The complex interactions of risk behaviors, differences in disease rates by race/ethnicity, and the impact of social environment on liver cancer suggests that community-based approaches to identifying high risk areas and high risk individuals within those areas, is warranted. We will discuss recommendations and reduction of risk behaviors in our educational session.

**F. Innovation.** This is the first study to apply a precision public health approach to address the growing burden of liver cancer and to engage community partners in this process.

#### 4.0 Study Design

In line with the Precision Medicine Initiative, we propose to utilize data from existing resources, to inform liver cancer prevention using cross-sectional data for the liver cancer geospatial analysis. Intervention materials include the development of an educational module addressing risk factors, symptoms, diagnosis and treatment. The sessions will incorporate both didactic and interactive modalities. The educational module includes a slide presentation, and will be accompanied by an educational brochure that participants can take home. The information included in the educational brochure reinforces the information presented in the slide show. Prior to each session, a pre-test will be administered to establish a baseline of knowledge and to collect demographic information. Following the education session, we will administer a posttest to evaluate the initial impact and assess participants' interest and impact of neighborhood health.

**4.1 Recruitment and Eligibility.** Eligible participants will self-identify at scheduled community events with identified community partners. They will be able to read and understand English or Spanish, and be 18 years or older. Participants must also be Philadelphia residents, or receive healthcare at a community partner site that is located in Philadelphia. Additional demographic data such as age and racial/ethnic background will be collected on the pre-survey.

Recruitment of participants during the COVID-19 pandemic will be adjusted to adhere to stay-athome and social distancing orders. These adjustments will include working with community partner sites to assist with the promotion of the liver study via a recruitment flyer to assist with identification of potential participants. Individuals interested in participating will contact FCCC staff directly at the number provided on the flyer or provide the partner with permission for us to contact them. We may also contact participants from a previous study that gave us permission to contact them about future research opportunities (IRB #17-8005). Per our protocol, staff will identify themselves and let them know why we are calling and how we obtained their name. Former study participants who are being re-contacted will be reminded that they gave us permission during previous study participation. The ongoing COVID-19 pandemic has negatively impacted the research team's ability to recruit via standard methods originally proposed due the "stay-at-home" orders. Therefore, the team would like to explore the following two approaches to facilitate recruitment efforts:

- 1. Collaboratively working with Temple Physicians Inc., an existing partner, we have drafted an invitation letter to their patients promoting the study and requesting that interested individuals, contact the research team. No direct patient recruitment will be employed.
  - a. The TPI practices have been identified and categorized according to the priority methodology presented.
- 2. With the approval of a Fox Chase Cancer Center Facebook Community Outreach page, we will utilize passive recruitment practices to promote the study, utilizing the approved recruitment flyer, to invite interested participants to contact the research team member listed on the recruitment flyer[12].
  - a. The Community Outreach FB sites intended audience is FCCC Community Outreach partners and their networks;
  - No direct targeting of individuals will be administered. Interested participants will call the research team listed on the approved recruitment flyer or may click a link provided in the Facebook post to be taken to an opt-in survey in REDCap. The opt-in survey responses are only accessible by the study team;
  - c. No individual's personal data will be collected via FB;
  - d. No individual's online activity will be collected and retained by the investigators;
  - e. Online communications will be monitored to ensure no PHI is divulged.
  - f. Comments posted regarding participation will be allowed as long as no specific information that might jeopardize the study is posted i.e. responses to questions;
  - g. Online communications will be monitored by the Outreach team ([name], [name], [name]). Any negative comments or PHI will be blocked from public view. All negative comments will be collected and if appropriate, will be reported to the IRB.

We believe these additional strategies will expand our reach, potentially benefitting our recruitment efforts. While the FB approach may garner a broader audience that our priority areas, we will continue to utilize the eligibility criteria stated, remaining focused on Philadelphia County. We will monitor and assess the overall impact of our new approaches as part of the data analysis and manuscript development.

This protocol is registered on clinicaltrials.gov, and eligible individuals who reach out to the study contact ([name]) listed on the study profile will also be recruited.

Participants recruited during the COVID-19 pandemic will also be asked if they have reliable telephone access and if they have access to a computer; due to suspension of in-person recruitment, the study will be conducted over the telephone and/or via Zoom or a similar platform.

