## 4.4 Study Procedures

**A. Recruitment and Informed Consent.** The Office of Community Outreach (OCO) has a history of working with multiple community organizations, offering free bilingual education via our community speakers bureau. During our education sessions, community partners coordinate logistics, promote our programs and invite community members to participate. Recruitment of study participants will occur working through these long-standing community partners. Partner sites will promote the study and invite participants to a session to learn more. A recruitment flyer may be used at some sites to advertise the study.

Recruitment efforts will be concentrated in census tracts with the greatest need for intervention, i.e., census tracts identified as high-risk due to socioeconomic factors linked to liver cancer (e.g., % non-Hispanic Black, household stability) and high rates of liver cancer. If no current partners are located in these high-risk census tracts, potential new partners will be identified by searching for community centers, federally qualified health centers, etc.

Individuals who attend the session will be informed about the scope of the study and invited to formally participate by the study team. Individuals interested in participating will be consented by health educator [name], project manager [name], or Co-PI [name] prior to completing the pre-intervention survey. Persons not interested will be thanked for their time and excused. We anticipate recruiting between 50-100 participants, depending on the number of participating community partners and the number of education session completed. Education sessions may be conducted on a one-on-one basis or in a group, depending on the number of interested individuals present at any given session. Individuals who refuse to participate or who withdraw from the project will be treated without prejudice.

Due to the COVID-19 pandemic, in-person recruitment efforts conducted by OCO has ceased. During pandemic-related closures, all study-related activities will be conducted over the phone, online, and through US mail. Recruitment will be conducted over the telephone, and informed consent will be obtained verbally (also over the telephone). Once informed consent is obtained, an oral consent document will be sent via US mail to the participant.

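### Does Section 14 need a defined report of where participants live and how they were recruited?

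*Combined protocol and SAP*

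**What the plan says.** **Targeting.** Section 1.0 sets out to work by "identifying neighborhoods with higher than expected rates of liver cancer and related risk factors and administering an educational intervention in those communities". The Aim 1 hypothesis in Section 2.0 is that better spatial tools "will inform resource allocation through more precise identification/targeting of communities in need".

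**Eligibility.** Section 4.1 is wider than the target tracts: "Participants must also be Philadelphia residents, or receive healthcare at a community partner site that is located in Philadelphia".

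**Recruitment.** Section 4.1 adds practice letters, a Facebook page, re-contact of people from an earlier study, and contacts through the trial registry listing. On Facebook it says "The Community Outreach FB sites intended audience is FCCC Community Outreach partners and their networks". It also concedes: "FB approach may garner a broader audience that our priority areas, we will continue to utilize the eligibility criteria stated, remaining focused on Philadelphia County". It then promises: "We will monitor and assess the overall impact of our new approaches as part of the data analysis and manuscript development".

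**High-risk areas.** Section 3.0 D says a new metric could show "which areas with high rates of liver disease (liver cancer, HCV, and/or HBV) also have a high disparity score". Section 4.4 A directs recruitment to "census tracts identified as high-risk due to socioeconomic factors linked to liver cancer", together with high liver cancer rates. Section 14.1 uses a spatial scan statistic to find clusters of liver cancer.

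**Analysis.** Section 4.4 B geocodes participants' street addresses for neighborhood analysis. Section 14 holds the registry scan, descriptive demographics, pre-post differences with t or Wilcoxon tests, a power statement, and a note on the modifiable area unit problem. It has no table by tract status or recruitment route.

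**The concern.** Two analyses are promised outside Section 14 and do not appear in it. The registry scan in 14.1 does not stand in for them, because it uses cancer cases and not study participants. The delivery method tracked under Section 4.3 B (in-person, telephone, online) is not the recruitment route.

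Reach matters in a project that sets out to educate particular communities, and several of the later routes have no stated tract-level targeting. Without the share of participants living in high-risk tracts, a reader could not judge whether the target communities were reached. If that category were settled only after outcomes were seen, the reported share could be shaped by the choice. With three descriptions of a high-risk area and no cut-off, that seems possible.

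**Working it through.** **1. Does anything in the efficacy analysis depend on tract status or route?**

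Inputs from Section 14.3: standardized effect d of 0.3-0.4, 80% power, two-sided 5% error, 50 to 100 participants. For a paired comparison, n = ((1.960 + 0.842)/d)².

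| d | n, normal formula | n, exact t | Power at the planned size (exact t) |
|---|---|---|---|
| 0.4 | 50 | 52 | 79.2% at n = 50 |
| 0.3 | 88 | 90 | 84.4% at n = 100 |

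The minimum of 50 is reproduced for d = 0.4, and the ceiling of 100 is above what d = 0.3 needs. Tract status and recruitment route enter neither this calculation nor the pre-post mean difference in 14.2. Leaving them out of Section 14 therefore changes neither the estimate nor its power.

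**2. Are there three competing definitions?**

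| Section | Content | Function |
|---|---|---|
| 3.0 D | Liver cancer, HCV and/or HBV rates plus a disparity score | Background: what a new metric could be used for |
| 4.4 A | Socioeconomic factors and high liver cancer rates | Operational: where recruitment is concentrated |
| 14.1 | Scan statistic on liver cancer rates | Tool for the rate part |

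Section 14.1 supplies the cancer-rate component of 4.4 A and does not say that a cluster alone makes a tract high-risk. Those two are compatible. Sections 4.2 B (mainly race/ethnicity) and 4.2 D (hepatocellular cancer incidence) are close to 4.4 A. What remains is that 4.4 A is narrower than the background text, and that the supplied text gives no cut-off or combining rule. The figure in Section 2.0 is not shown, Table 1 cited in 3.0 D is not in the text, and the spatial work is tied to a separate approved protocol, so the rule may be written elsewhere.

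**3. Can the promised description be produced from what is planned?**

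Tract status: yes. The geocoding sentence in 4.4 B carries no restriction by mode of contact, so it covers addresses taken by telephone. Sign-in sheets are destroyed only once geocodes exist. Recruitment route: no passage names a field, but the promise in 4.1 cannot be kept without one.

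**4. Would a high-risk subgroup estimate add anything?**

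The documents do not give the share living in high-risk tracts, so it is assumed here. The 95% half-width in SD units is t(0.975, n−1)/√n.

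| Enrolled | Assumed share | n in subgroup | Half-width (SD) |
|---|---|---|---|
| 100 | 75% | 75 | 0.230 |
| 100 | 50% | 50 | 0.284 |
| 100 | 25% | 25 | 0.413 |
| 50 | 50% | 25 | 0.413 |

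At n = 25 the power is 0.30 for 0.3 SD and 0.48 for 0.4 SD. In the last two rows the interval is wider on each side than the effect the study is planned around, so the estimate could not support a conclusion there. The share itself is a plain count among the people enrolled. As a description of that sample it needs no interval.

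**The case for a change.** The strongest case for a change is timing. Recruitment route may be hard to reconstruct if nobody records it, and a tract rule that is not written down can drift. If 10 participants changed status under a different rule, the reported share would move by 10/100 = 10 points at the largest sample and 10/50 = 20 points at the smallest. One definition and one table would be cheap.

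Part of this stands. Section 14 does omit both items, and the supplied text does not fix a cut-off. The rest is weaker. Section 4.1 says the partner practices have already been categorized by a priority method, and 4.4 A uses high-risk tracts to direct recruitment, which suggests that a rule was in use before outcomes were analyzed. The count of 10 is an illustration and comes from no document. The plan contains no high-risk estimate whose result could be steered. Share by residence is not a stated endpoint either: Aim 2 concerns partnerships in high-risk areas, and eligibility deliberately admits people by where they receive care.

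**Conclusion.** No change to the plan is called for. The omission from Section 14 is real, but it is missing detail on descriptive reporting that the plan commits to elsewhere and that analysts can fill sensibly: count participants by tract status and route, using the tract rule that guided recruitment. The effect on the overall pre-post estimate, its test and the power statement is nil. A high-risk subgroup estimate would be an optional extra, with a half-width from 0.23 SD (75 of 100 participants) to 0.41 SD (25 participants) under the assumed shares.

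This rests on two assumptions. One is that recruitment route is recorded, as the promise in Section 4.1 implies. The other is that the rule used to prioritize tracts exists in the study's working documents or the linked protocol. If either failed, the study would say less about reach, but its result on the education session would be the same.
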